9.3.1. Packaging and Labeling

Before the shipment to the investigative sites, Investigational Product (IP) will be labeled with information required by regulatory agencies, such as a statement that it is limited to investigational use. Investigational Product to be administered to the subject will be labeled by the site after dose preparation by the unblinded pharmacist or designee in a manner that protects blinding.

9.3.2. Blinding

This clinical trial is double-blinded, meaning the subjects and site personnel are blinded to treatment assignment, except for the clinical trial site's unblinded pharmacist or designee. The study site must have a written plan in place to ensure blinding is adequately maintained for the study. If the blind is broken, the date, time, and reason must be recorded. The blind should only be broken for reasons in which knowledge of the treatment assignment is critical to the management of subject safety. The Principal Investigator will report any cases of unblinding to the Sponsor within 24 hours of the incident.

9.3.3. Storage and Handling of Investigational Product

Investigational Product/Placebo will be stored at a central depot or at the clinical site at -20°C (-10°C to -25°C) in accordance with any accompanying instructions. Please refer to the Pharmacy Manual for additional storage and handling procedures. Diluent (0.9% saline) will be stored according to manufacturer instructions.

Investigators shall take adequate precautions, including storage of the Investigational Product and Placebo in a securely locked, substantially constructed cabinet or other securely locked, substantially constructed enclosure, access to which is limited to maintain blind, prevent theft or diversion of the substance into illegal channels of distribution.

9.3.4. Accountability and Disposition of Investigational Product

The Investigator is responsible for maintaining accurate Investigational Product accountability records throughout the clinical trial. The site must maintain an Investigational Product Accountability Log as instructed in the Pharmacy Manual. Where more than one secure area is being used for storage at a site, all movement of Investigational Product through the chain of custody must be recorded in accountability records such that full reconciliation may be completed at the end of the trial.

Included with each Investigational Product shipment is a form listing lot numbers and quantity shipped. The Investigator, responsible pharmacist, or designee, will sign and return to Alder BioPharmaceuticals, Inc., or designee, a statement that certifies the receipt and integrity of these supplies. A copy will be retained for the site clinical trial file.

After completion of the clinical trial, the Investigator is responsible for either returning or destroying all unused Investigational Product. The Investigator must verify that no remaining supplies are in his/her possession. All used/partially used vials/IV bags will be destroyed onsite according to the site SOPs, or returned according to Alder BioPharmaceuticals, Inc. directive. Destruction must be in accordance with local regulations for the product type.

If the clinical trial is terminated, suspended, discontinued, or completed, the Investigator or designee shall return the unused supplies to the Sponsor or designee, or otherwise provide for disposition of the unused supplies (as authorized by the Sponsor).

9.4. Concomitant Medications

Any concomitant therapy used from the time the subject signs the informed consent form through Week 32 must be recorded on the eCRF, including medications required for treatment of any AEs or SAEs. The medication name, dosage, date, and indication for use must be recorded. The Medical Monitor or designee should be notified in advance of (or as soon as possible after) any instances in which restricted therapies are administered.

The following medications are **restricted** through Week 24:

- Barbiturates and prescription opiates are allowed for ≤ 4 days per month through Week 24, provided the subject has been on a stable regimen (≤ 4 days per month) for at least 2 months prior to screening.

- Any botulinum toxin injections for migraine or for any other medical/cosmetic reasons are prohibited within 4 months prior to screening and during the trial through Week 24.
- Devices, neuromodulation, neurostimulation, or injectable therapy (trigger point injections) for headache prophylaxis are prohibited 2 months prior to screening and during the trial through Week 24.
- Monoamine oxidase inhibitors (MAOIs), ketamine, methysergide, methylergonovine, and nimesulide are prohibited within 3 months prior to screening and during the trial through Week 24.

Any hormonal therapy (e.g., contraceptives, hormone replacement therapy) use must be stable for 3 months prior to screening and remain stable during the trial through Week 32.

Medications taken for headache prophylaxis will be permitted provided that the dose has been stable for at least 3 months prior to screening and there are no alterations to their regimen through Week 24. In general, changes to prophylactic headache medications during the trial are not allowed through Week 24. At the discretion of the Investigator, on a case by case basis, changes to the regimen that might be clinically warranted may be made prior to Week 24 after consulting with the Medical Monitor and obtaining approval.

Sites are required to indicate if a medication is used for prophylaxis purposes or if it is used for the acute treatment of migraines. The Investigator should reevaluate the patient's risk factors relative to the prescribing information for both prophylactic and acute treatments that the patient is using, and judge that the use of these medications continues to be considered safe.

10. STUDY ASSESSMENTS AND PROCEDURES

10.1. Schedule of Assessments

Assessment and procedures at each visit are summarized in Section [2](#) - Schedule of Events and Assessments.

10.2. Assessments and Procedures

10.2.1. Randomization

Randomization must occur after the subject completes the 28-day eDiary screening period. Every effort should be made to conduct an onsite randomization visit; however, a phone visit is acceptable in cases where the subject's schedule will not permit an onsite visit.

All subjects will be randomized via the IWRS (Interactive Web Response System) after the following:

- Eligibility has been approved by the Medical Monitor
- Review of all inclusion/exclusion criteria to confirm subject continues to meet inclusion/exclusion criteria.
- Verification that subject meets eDiary-related eligibility criteria as calculated within the eDiary portal.
- Subject confirms continued interest in participating in the study.

10.2.2. Demographics

The year of birth, age, sex, ethnicity, race, and how the subject was recruited to the study will be collected in source records and in the CRF.

10.2.3. Medical History

Significant historic and current medical conditions or illnesses, allergies to medications, and prior surgical interventions will be recorded in the source records and in the CRF. Symptoms that are ongoing at the time of informed consent will be considered medical history.

Migraine history will also be collected in the source records and the CRF, including age at diagnosis of chronic migraine as well as other details of the subjects' history with migraine. If

the subject is not a current or past user of a prescribed or over-the-counter medication for migraine, the Medical Monitor will be consulted.

Investigators should demonstrate due diligence in trying to obtain medical records. All attempts to obtain medical records should be documented. If medical records cannot be obtained, history may be confirmed via patient interview in order to obtain sufficient information to confirm all eligibility criteria are met.

10.2.4. Physical Examinations

Physical examinations will be performed at the times noted in the Schedule of Events and Assessments in Section 2 and must be performed by an Investigator who has been trained and delegated the task on the Delegation of Authority Log.

The physical examination at the screening visit will be comprehensive and appropriate to determine the overall physical health of each subject. Examination of the genitourinary system and rectum may be deferred by the Investigator if the subject's related medical history and review of systems are negative. For all other visits that call for a physical examination, the body systems examined will be at the discretion of the Investigator.

Each physical examination will include weight measurement. Height will be measured at screening only.

Abnormal physical examination findings at the screening visit will be recorded as medical history. Any new or worsening physical examination finding identified after informed consent will be considered an AE.

10.2.5. Vital Signs

Vital signs, including blood pressure (BP) and pulse, will be measured at the time points specified in the Schedule of Events and Assessments in Section 2.

When measuring vital signs, the subject should be seated comfortably, with back supported and rested for 5 minutes before obtaining vital signs. Blood pressure may be repeated to confirm measurement.

For BP measurements, the subject should have their upper arm positioned so that it is level with their heart and feet flat on the floor. Excess clothing that might interfere with the BP cuff or

constrict blood flow in the arm should be removed. A blood pressure cuff of appropriate size should be wrapped around the bare upper arm such that the bladder portion of the cuff extends at least 80% around the arm. The center of the bladder should be in line with the brachial artery so as to allow the stethoscope diaphragm clear access to the brachial artery. Site staff and subject should refrain from talking during the reading.

10.2.6. Questionnaires

Questionnaires should be administered to subjects in the order listed below. On Day 0 and Week 12, all questionnaires should be administered prior to dosing.

Protocol number, subject number and date of administration must be captured on all questionnaires. All questionnaires completed by subjects must be reviewed for completeness and clarity by site staff prior to the subject leaving the clinic. The subject should be asked to complete any unanswered questions.

10.2.7. Columbia-Suicide Severity Rating Scale (C-SSRS)

The C-SSRS will be administered by trained (i.e., C-SSRS certified) site staff at the time points specified in the Schedule of Events and Assessments in Section 2. The C-SSRS must be administered prior to dosing at dosing visits (Day 0 and Week 12).

The C-SSRS “Baseline/Screening” version will be used for the Screening Visit, and the C-SSRS “Since Last Visit” version will be used for all subsequent visits.

10.2.8. Most Bothersome Symptom (MBS)

The Investigator will verbally obtain the most bothersome symptom associated with the subject’s migraines during the screening visit. The most bothersome symptom will be captured in the eCRF and may include nausea, vomiting, sensitivity to light, sensitivity to sound, mental cloudiness, fatigue, pain with activity, mood changes, or other migraine-related symptom.

At each subsequent visit, the site staff will provide the questionnaire along with the other subject-completed questionnaires as specified in the Schedule of Events and Assessments in Section 2.

10.2.9. Other Questionnaires

The following questionnaires will be administered at days and times provided in the Schedule of Events in Section 2. Subjects will be given the questionnaires in the order specified below and asked to review the brief instructions on each questionnaire and complete.

- Patient Global Impression of Change (PGIC)
- Short-Form Health Survey (SF-36)
- Health-Related Quality of Life (EQ-5D-5L)
- Headache Impact Test (HIT-6)

10.2.10. 12-Lead ECG

ECGs will be performed using a 12-lead ECG device provided for the study at the time points specified in the Schedule of Events and Assessments in Section 2. On Day 0 and at Week 12, ECG must be performed pre-dose, and within 2 hours post-dose. ECG data will be transmitted and read centrally by a cardiologist; however, the Investigator must review the ECG prior to dosing and ensure there are no clinically significant abnormalities prior to dosing. In addition, all confirmed (i.e., centrally-read) ECGs will be reviewed by the Investigator and evaluated for clinical significance in a timely manner.

All ECGs are expected to be performed on the ECG device provided to the site by the trial Sponsor. A local ECG device may be used only in the event that there are technical issues with the central ECG device that cannot be resolved while the subject is onsite. If a local ECG device is used, a paper ECG must be submitted to the ECG vendor for central reading. All technical issues must be reported immediately to the ECG vendor help desk.

10.2.11. Laboratory Samples and Testing

10.2.11.1. Urine Drug Screening

Drugs of abuse screening test will be performed on urine samples during the screening visit. Urine drug screen kits will be provided by the central lab and the test performed on site. If a urine drug screen is positive and there is no medical record documentation of prescribed medications to explain the result, the subject should be considered for exclusion from the study. Questions regarding the eligibility can be addressed with the Medical Monitor.

10.2.11.2. Pregnancy Testing

Urine pregnancy tests will be performed for all female subjects, regardless of childbearing potential, at the specified time points in the Schedule of Assessments, Section 2. On Day 0 and at Week 12, urine pregnancy test must be performed prior to dosing.

Urine pregnancy test kits will be provided by the central lab, and the test performed on site.

The contraceptive method used by females of child-bearing potential and males with partners of child-bearing potential must be confirmed with the subject and recorded in the source record at screening, and reconfirmed with the subject and recorded in the source record at each subsequent study visit.

10.2.11.3. Clinical Laboratory Testing

Blood samples for clinical laboratory tests, including hematology, serum chemistry and serology (including HIV, Hepatitis B and Hepatitis C), will be collected at the time points specified in the Schedule of Events and Assessments in Section 2. Clinical laboratory tests performed are listed in Section 11.1.7.

All clinical laboratory blood samples will be initially processed by site staff and shipped to a central laboratory for analysis as specified in the Laboratory Manual. An Investigator listed on the Form FDA 1572 will review all lab reports and document clinical significance for any out-of-range lab value(s) listed in the report.

10.2.11.4. Pharmacokinetic and Immunogenicity Sampling

Blood samples will be collected for the analysis of plasma PK of ALD403 and for determination of anti-ALD403 antibodies in serum (immunogenicity) at specified time points in the Schedule of Events and Assessment in Section 2. All samples will be initially processed, stored, and shipped as specified in the Laboratory Manual.

10.3. eDiary Completion and Compliance Review

The subject will be instructed to complete an electronic diary (eDiary) daily from screening through Week 24.

The eDiary will be distributed to each subject at the screening visit after subject training on eDiary use by site staff. The day of eDiary distribution will start the 28 day eDiary screening

period. The subject will record information daily regarding headache characteristics, severity, and length. During the screening period, an eDiary Eligibility Report will summarize baseline headache and migraine days and eDiary compliance. The headache and compliance data from the eDiary will also be made available to the clinical site for review on a regular basis via the eDiary system portal.

Subject eligibility will be confirmed prior to randomization. Any subject found to be ineligible for the study during the screening period or prior to randomization or dosing will not be randomized or dosed.

Site staff will monitor each subjects eDiary compliance on an ongoing basis through Week 24, and will counsel subjects as needed on the on the importance of completing the eDiary daily. All follow-up with subjects regarding eDiary compliance should be documented in the source records.

During the Week 24 visit, or Early Termination visit if subject discontinues prior to Week 24, eDiary closeout must be performed while the subject is on site.

11. ASSESSMENT OF SAFETY

11.1. Adverse Events

11.1.1. Definitions

An adverse event (AE) is any untoward medical occurrence in a patient or clinical investigation participant administered a pharmaceutical product that does not necessarily have a causal relationship with the treatment. An AE can therefore be any unfavorable and unintended sign (including an abnormal laboratory finding), symptom, or disease temporally associated with the use of a medicinal (investigational) product, whether or not related to the medicinal (investigational) product. (ICH E6)

11.1.2. Assessment of Adverse Events

The Investigator is required to monitor the occurrence of adverse events for each subject from the time of informed consent through the course of the clinical trial. Adverse events may be reported by the subject, reported by a caregiver, or reported by the investigative site through Investigator site personnel open-ended questioning, through physical examination, laboratory test, documentation in medical records, or by other means. Adverse events include:

- Any new undesirable medical experience or an unfavorable and unintended change of an existing condition that occurs during or after treatment, whether or not considered related to the Investigational Product.
- Any abnormal assessment or laboratory findings considered by the Investigator to be clinically significant. Clinically significant findings include but are not limited to those that lead to discontinuation or interruption of study treatment, require therapeutic intervention, or require a change in subject management.

A new or worsening of a pre-existing or chronic condition is considered an adverse event and must be reported as such. Medical conditions, which existed prior to the time of informed consent into the clinical trial, will not be considered an adverse event unless the condition worsens. Unchanged, chronic, non-worsening or pre-existing conditions from the time of informed consent are not adverse events and should not be recorded on the AE eCRF.

Pre-existing medical conditions of clinical significance must be included in the subject's medical history and recorded on the medical history eCRF page.

Each event recorded on the AE eCRF is required to be assessed by the Investigator with regard to the following; seriousness, severity, and relationship to Investigational Product, as outlined below.

Seriousness

An adverse event or suspected adverse event is considered serious if in the view of either the Investigator or Sponsor, it results in;

- Death
- Is life-threatening (this means that the subject is at risk of death at the time of the event; it does not mean that the event hypothetically might have caused death if it were more severe)
- Inpatient hospitalization or prolonged existing hospitalization
- A persistent or significant incapacity or substantial disruption of the ability to conduct normal life functions.
- Congenital anomaly/ birth defect
- Important medical events that may not result in death, be life-threatening or require hospitalization may be considered serious when, based upon appropriate medical judgement, they may jeopardize the patient or subject and/or may require medical or surgical intervention to prevent one of the outcomes listed in the definition (21 CFR 312.32(a) and ICH E2A).

Of note:

- A social hospitalization (i.e., hospitalizations for pre-admissions not due to an acute medical issue) is not considered an SAE
- Hospitalization is considered a greater than 24 hour hospital admission.

Severity

The severity of an AE will be graded as follows:

- Grade 1 Mild; asymptomatic or mild symptoms; clinical or diagnostic observations only; intervention not indicated.

- Grade 2 Moderate; minimal, local or noninvasive intervention indicated; limiting age-appropriate instrumental Activities of Daily Living (ADL).
- Grade 3 Severe or medically significant but not immediately life-threatening; hospitalization or prolongation of hospitalization indicated; disabling; limiting self-care ADL.
- Grade 4 Life-threatening consequences; urgent intervention indicated.
- Grade 5 Death related to AE.

Relationship to Investigational Product

The Investigator is required to assess the causality/relationship between each AE and the Investigational Product as not related or related and record the assessment on the source documents and in the eCRF AE page. Medical judgment should be used to determine the likely relationship of the AE to the Investigational Product considering all relevant factors including (but not limited to) relevant history, concomitant medical condition and concomitant medications. Determination should be based on assessment of temporal relationships, biologic plausibility, association (or lack of association) with underlying disease, and presence (or absence) of a more likely cause.

Not Related: It is plausible that the AE has an etiology other than the Investigational Product (e.g., pre-existing condition, underlying disease, concomitant medical condition, or concomitant medication).

Related: The AE cannot reasonably be explained by the subject's clinical state, concomitant medical condition or concomitant therapies, and a temporal relationship exists between the event onset and administration of the Investigational Product.

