11.1.3. Recording Adverse Events

Event reporting will extend from time of informed consent until completion of the final visit. Serious adverse events occurring after the end of the clinical trial must be reported if the Investigator considers there to be a causal relationship with the Investigational Product.

SAE Notification Form should be used to report any related SAEs which occur after the end of the clinical trial.

Adverse events (AEs) should be recorded on the AE eCRF, whether believed by the Investigator to be related or not related to the Investigational Product.

AE reporting should contain:

- A brief description of the event
- Date of onset
- Date of resolution
- Severity
- Actions taken or treatment required
- Relationship to Investigational Product
- Outcome
- Whether the event is considered serious

Whenever possible, the Investigator should group signs or symptoms that constitute a single diagnosis into a single event term. For example, “cough, rhinitis, and sneezing” might be grouped together as “upper respiratory tract infection.”

Asymptomatic abnormal findings considered by the Investigator to be clinically significant should be recorded as an AE, unless it is associated with a clinical syndrome that has already been reported as an AE.

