11.1.5. Unexpected and Related Serious Adverse Events

Unexpected SAEs are those which:

- Are not previously reported as associated with ALD403, as referenced in the Investigator's Brochure.
- May be symptomatically and pathophysiologically related to an AE listed in the Investigator's Brochure, but differ from the event due to greater severity, frequency or specificity.

The Sponsor or designee will report, to the appropriate regulatory authorities according to local and regulatory requirements, unexpected SAEs which are considered related to ALD403 (suspected unexpected serious adverse reactions [SUSARs]). The clinical trial site personnel are responsible for reporting these events to their EC/IRB in accordance with applicable local and regulatory requirements.

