3.6. Analysis of Safety Endpoints

3.6.1. Adverse Events

Adverse events are collected from the time of Informed Consent through the final subject visit. The incidence of all AEs and study drug-related AEs will be tabulated by treatment received. These AEs will be classified by system organ class and preferred term using the MedDRA. For incidence reporting, if a subject reported more than 1 AE that was coded to the same preferred term/system organ class, the subject will be counted only once for that specific preferred term/system organ class. Events recorded between the time the informed consent is signed and the first Investigational Product administration will be listed.

A treatment-emergent AE (TEAE) is an AE with a start date and time on or after the date and time of the treatment.

For the purpose of inclusion in TEAE tables, incomplete AE onset and end dates will be imputed as follows:

Missing onset dates (where UK and UKN indicate unknown or missing day and month respectively):UK-MMM-YYYY: If the month and year are different from the month and year of the first dose of trial drug, assume 01-MMM-YYYY. If the month and year are the same as the first dose of trial drug month and year, and the end date (after any imputation) is on or after the first dose of trial drug, then assume the date of the first dose of trial drug. If the month and year are the same as the first dose of trial drug month, and year and the end date (after any imputation) is prior to the first dose of trial drug, then assume the end date for the onset date.

- DD-UKN-YYYY/UK-UKN-YYYY: If the year is different from the year of first dose of trial drug, assume 01-JAN-YYYY of the collected year. If the year is the same as the first dose of trial drug year, and the end date (after any imputation) is on or after the first dose of trial drug, then assume the date of the first dose of trial drug. If the year is the same as the first dose of trial drug, and the end date (after any imputation) is prior to the first dose of trial drug, then assume the end date for the onset date.

Missing end dates (where UK and UKN indicate unknown or missing day and month respectively):

- UK-MMM-YYYY: Assume the last day of the month;
- DD-UKN-YYYY/UK-UKN-YYYY: Assume 31-DEC-YYYY.

An overview of AEs, which includes subject incidence of TEAEs, study drug-related TEAEs, Serious TEAEs, TEAEs leading to study treatment interruption, TEAEs leading to study drug discontinuation and deaths will be presented.

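### The causality definitions force any event with both a plausible drug cause and a plausible other cause into Not Related, contradicting the protocol's own weighing instruction

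*Protocol*

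**What the plan says.** Protocol section 11.1.2 requires the investigator to "assess the causality/relationship between each AE and the Investigational Product as not related or related". There is no middle category. The two definitions are:

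- *Not Related*: "Not Related: It is plausible that the AE has an etiology other than the Investigational Product", with pre-existing condition, underlying disease, concomitant condition and concomitant medication as examples.
- *Related*: "The AE cannot reasonably be explained by the subject's clinical state, concomitant medical condition or concomitant therapies, and a temporal relationship exists" between onset and administration.

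Just before these definitions, the same section asks for medical judgment based on timing, biologic plausibility, "association (or lack of association) with underlying disease, and presence (or absence) of a more likely cause".

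The resulting code is then used in three places:

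- Protocol 11.1.3: SAEs after the end of the trial "must be reported if the Investigator considers there to be a causal relationship with the Investigational Product".
- Protocol 11.1.5: the sponsor or its designee reports to regulators those unexpected SAEs that are considered related to ALD403.
- SAP 3.6.1: "The incidence of all AEs and study drug-related AEs will be tabulated by treatment received", and treatment-related TEAEs are summarized by system organ class and preferred term. SAP 3.6.2.1 also tabulates adverse events of special interest by relationship.

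**The concern.** A causality field matters most for the ambiguous event, where the drug could be responsible but so could something else. The definitions settle every such event the same way, as *Not Related*, however closely it follows the infusion. The preceding sentence asks for something different: a comparison of how likely the competing causes are. Two investigators relying on different sentences of one section can code the same event in opposite ways.

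Ambiguous events should not be rare here. Inclusion criterion 5 (Protocol 8.1) requires that acute or prophylactic migraine medication has been prescribed or recommended, and Protocol 9.4 permits stable prophylactics. Concomitant medication is one of the listed grounds for *Not Related*.

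Safety of repeat doses is a secondary objective (Protocol 6.2), and Protocol 5.4 says that long-term data are limited. At stake are the reporting of late serious events and the meaning of every table built on the relationship field.

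**Working it through.** No arithmetic applies; the check is a reading of the definitions against each other, followed by a trace of where the code is used.

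**Step 1. Apply the definitions to the four possible cases**, each with timing that fits:

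| Drug plausible? | Other cause plausible? | Code under the definitions |
|---|---|---|
| Yes | No | Related |
| Yes | Yes | Not Related |
| No | Yes | Not Related |
| No | No | Related |

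The code follows the second column alone. Once timing fits, whether the drug is a plausible cause makes no difference. The second row is the problem.

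This reading treats a plausible alternative as a reasonable explanation. If someone separates the two ideas, an event whose alternative cause is plausible but not a reasonable explanation would meet both definitions at once, which is no better.

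**Step 2. Compare with the weighing instruction.** It asks about the "presence (or absence) of a more likely cause", which is a comparative test. Under it, a second-row event is *Related* when the drug is the likelier cause. The definitions never ask which cause is likelier, so the two parts of section 11.1.2 disagree on this row.

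**Step 3. Trace the consequences.**

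- *Post-trial SAEs (Protocol 11.1.3).* The investigator's causal judgment is the only stated condition for reporting, so a mixed-cause SAE need not be reported. The effect is direct. Antibody-positive subjects can be asked for samples for up to 6 months after the last visit (Protocol 12.3), so some subjects remain in contact with sites in that period.
- *Related-event tables (SAP 3.6.1, 3.6.2.1).* The effect is direct: second-row events are missing from the related subset.
- *SUSARs (Protocol 11.1.5).* An event must be considered related, and section 11.1.2 holds the only causality standard in the documents. But section 11.1.5 does not say whose view counts. Under Protocol 11.1.4 all in-trial SAEs are reported within 24 hours whatever the relationship, the Medical Monitor or designee reviews them, and the sponsor decides on expedited reporting. A SUSAR can be missed, but the definitions alone do not cause it. For seriousness, Protocol 11.1.2 lets either the investigator or the sponsor decide; no matching rule exists for causality.

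**Step 4. Identify what does not depend on the code.** All AEs are recorded whether related or not (Protocol 11.1.3). All-causality AE, TEAE and SAE summaries by treatment are produced (SAP 3.6.1, 3.6.2.2). Events of special interest are selected by coded term, and infusion events also by timing (SAP 3.6.2.1).

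**The case against.** The strongest reply is that the trial's safety conclusions do not rest on this field. In a blinded, placebo-controlled trial the comparison that answers the safety objective is the all-causality one between arms, and it is intact. A data monitoring committee reviews safety data (Protocol 7.3, SAP 2.7.4). Only the related subset suffers, under the same rule in every arm. This stands, and it limits the point. A reader might infer that the safety evaluation as a whole is biased towards finding nothing; the documents do not support that.

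A reader might also infer that mixed-cause SAEs automatically drop out of SUSAR reporting. Protocol 11.1.4 shows otherwise, as set out above.

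A third tempting inference is that an allergic-type event soon after infusion would be hidden if the subject had also taken another medicine. It would not. Urticaria within one week of dosing is an event of special interest by term and timing. Protocol 11.2 sends potential allergic reactions to the Medical Monitor, and potential systemic ones to extra blood sampling, without reference to the relationship code.

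Finally, it can be said that medical judgment will soften the definitions in practice. It may, but the definitions state what each category means, and an investigator who follows them literally is complying with the protocol. This part of the reply does not remove the defect.

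**Conclusion.** The concern holds as an internal contradiction with two direct effects: mixed-cause SAEs after the end of the trial need not be reported, and the drug-related AE and TEAE tables and the by-relationship tables of special-interest events are understated. A missed SUSAR is possible but not automatic. The randomized all-causality comparison, the term-based selection of special-interest events, the efficacy analyses and the power are unaffected.

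The size cannot be given as a number. A reader might assume that some share *a* of drug-caused events also has a plausible alternative cause, and conclude that the share *a* is miscoded. That only returns the assumption, and the documents do not supply *a*. The common events in Protocol 5.4 were seen on ALD403 or placebo, so they say nothing about drug-caused events in particular. The comorbidity described in Protocol 5.2 concerns chronic migraine in general, while Protocol 8.2 excludes several such conditions.

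The conclusion assumes that investigators apply the definitions as written. It should be corrected, since following the rule as written misclassifies the ambiguous events.

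**What to change.** Replace the two definitions with a pair in which one is the negation of the other, and keep the existing list of factors to weigh:

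- *Related: there is a reasonable possibility that the Investigational Product caused or contributed to the AE, even if another cause is also possible.*
- *Not related: there is no such reasonable possibility.*

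No clause about a more likely alternative should be added to the second definition. An event with a likelier other cause and a reasonable possibility of drug contribution would then fit both.

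In Protocol 11.1.5, state that an SAE counts as related for SUSAR purposes if either the investigator or the sponsor considers it related, matching the rule for seriousness in 11.1.2.

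The text change is small, but it is an amendment, with ethics committee approval where appropriate (Protocol 14.8), communicated to approximately 150 centers, and the eCRF completion guidance must follow. More events will be coded related in all arms, including placebo, and there will be a few more expedited reports. Because site assessors are blinded (Protocol 9.3.2), the broader definition should not itself favour an arm. If the change is made mid-trial, the related-event tables should note its date, because the field means different things before and after.
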